6.2 Preparation/handling/storage/accountability

The Investigator or designee must confirm appropriate temperature conditions have been maintained during transit for all study treatment received and any discrepancies are reported and resolved before use of the study treatment.

Only participants enrolled in the study may receive study treatment and only authorised site staff may supply or administer study treatment. All study treatments must be stored in a

secure, environmentally controlled, and monitored (manual or automated) area in accordance with the labelled storage conditions with access limited to the Investigator and authorised site staff.

The Investigator, institution, or the head of the medical institution (where applicable) is responsible for study treatment accountability, reconciliation, and record maintenance (ie, receipt, reconciliation, and final disposition records).

Further guidance and information for the final disposition of unused study interventions are provided in the Pharmacy Manual.

6.2.1 Preparation and Handling of Investigational Product

The IP will be administered at the study site, on treatment visits, and within visit windows as specified in the SoA ([Table 2](#)). The IP will be supplied to the site in kits with an APFS of either benralizumab or placebo. Each kit will have a unique identifier (ID) that is printed on all labels within the kit (ie, the outer carton label and the label of each container within the carton).

Only participants randomised to the study may receive IP and only authorised site staff may dispense and administer IP.

6.2.2 Shipping and Storage

All shipments of IP include a data logger which will allow the Investigator, or designee, to confirm that appropriate temperature conditions have been maintained during transit for all IP received. Any discrepancies must be reported and resolved before use of the IP.

In the following cases, the site staff should not use affected IP and should immediately contact the AstraZeneca representative for further guidance:

- Temperature excursion upon receipt or during storage at the study site
- Damaged kit upon receipt
- Damaged syringe/cartridge

Damaged or temperature excused IP should be documented using the IVRS/IWRS (please refer to IVRS/IWRS manual and the Pharmacy manual for further details).

All IP (ie, benralizumab and matching-placebo) must be stored in a secure, environmentally controlled, and monitored (manual or automated) area, in the original outer container. The IP (ie, benralizumab and matching-placebo) must be kept under conditions specified on the label (refrigerated between 2°C to 8°C [36°F to 46°F], protected from light, and must not be frozen), with access limited to the Investigator and authorised site staff. The temperature should be monitored on a daily basis and documented in the temperature monitoring log.

6.2.3 Accountability

The Investigator, institution, or the head of the medical institution (where applicable) is responsible for IP accountability, reconciliation, and record maintenance (ie, receipt, reconciliation, and final disposition records).

A site monitor will account for all IP received at the site, for unused IP, and for appropriate destruction of unused study treatments. Any unused kits will be destroyed locally (for further details, refer to the Pharmacy Manual). Documentation of IP delivery and destruction should be maintained according to applicable AstraZeneca and institution procedures.

Further guidance and information for the final disposition of unused study treatment are provided in the Pharmacy Manual (provided to the sites). In the case of a malfunctioning IP APFS device, the site should contact the study monitor to initiate a product complaint process according to applicable guidelines.

6.3 Measures to Minimise Bias: Randomisation and Blinding

6.3.1 Randomisation

All participants will be centrally assigned to randomised IP using an IVRS/IWRS. Randomisation codes will be assigned strictly sequentially in each stratum as participants become eligible for randomisation. Randomisation will be stratified by region. Participants who fail to meet the inclusion/exclusion criteria should not, under any circumstances, be randomised or receive IP. There can be no exceptions to this rule. Participants may be rescreened under certain conditions (Section 5.4.1).

If a participant withdraws from the study, then his/her enrollment/randomisation code cannot be reused unless the participant is rescreened. Withdrawn participants will not be replaced.

6.3.2 Blinding

Benralizumab and placebo will not be visually distinct from each other. All packaging and labelling of the IP will be done in such a way as to ensure blinding for all AstraZeneca, AstraZeneca representative and investigational site staff. Neither the participant nor any of the Investigators, AstraZeneca or the AstraZeneca representative staff who are involved in the treatment, clinical evaluation, and monitoring of the participants will be aware of the treatment received. Since benralizumab and placebo are not visually distinct, IP will be handled by an appropriately qualified member of the study team (eg, pharmacist, Investigator, or designee) at the site.

Benralizumab is available only as a 30 mg dose in a prefilled syringe. Since the 60 mg treatment requires 2 SC injections, all participants will receive 2 injections during the initial 12-week treatment period (ie, at Visits 2, 3, and 4) to maintain the blind:

- Participants randomised to the benralizumab 30 mg group will receive one benralizumab 30 mg injection and one placebo injection
- Participants randomised to the benralizumab 60 mg group will receive 2 benralizumab 30 mg injections
- Participants randomised to the placebo group will receive 2 placebo injections

All participants will receive one SC injection at Visit 5 through Visit 16 (End of Treatment [EOT]). During the extension period, participants receiving benralizumab 30 mg Q8W will receive a placebo injection at every other site visit; thus, the investigational staff, participants, and AstraZeneca will remain blinded to the participant's dosing regimen (refer to Section 4.1.2 for details on dosing regimens).

A site monitor will perform IP accountability. If the treatment allocation for a participant becomes known to the Investigator or other study staff involved in the management of study participants or needs to be known to treat an individual participant for an AE, the AstraZeneca representative must be notified promptly by the Investigator and before unblinding (if possible).

The following personnel will have access to the randomisation list during the study, prior to the primary DBL:

- Those generating the randomisation list
- Personnel at the IWRS/IVRS company
- The AstraZeneca supply chain department
- Participant safety department at AstraZeneca
- Bioanalytical laboratory performing the PK and ADA sample analysis

The information in the randomisation list will be kept from other personnel involved in the conduct of the study in a secure location until the after primary DBL. No other member of the extended study team, including AstraZeneca, or any Contract Research Organisation handling data, will have access to the randomisation scheme during the conduct of the study.

Maintaining the Blind to the Participant's Blood Eosinophil and Basophil Counts and Blood eosinophil-derived neurotoxin (EDN) Level

Participants on active benralizumab treatment are expected to have lower eosinophil and basophil blood counts and lower levels of blood EDN than participants on placebo based on its established mechanism of action. Procedures to prevent unblinding based on eosinophil and basophil counts and blood EDN levels will be in place during the induction, maintenance, and extension treatment periods (from Week 0 through Week 52):

- Haematology assessments will be conducted by a central laboratory. Post-randomisation (beginning at Visit 2, Week 0), AstraZeneca, study site personnel, and participants will be blinded to the eosinophil and basophil counts. The absolute eosinophil, basophil, and monocyte counts, and percentages will be redacted from the haematology reports provided to the investigational sites; absolute neutrophils and absolute lymphocytes will be provided.
- If the Investigator orders any local safety laboratory assessments, the requested tests should be restricted to the question at hand. For example, if haemoglobin is desired, the Investigator should avoid ordering a complete blood cell count with a differential count.
- In cases where the Investigator requires an eosinophil, basophil, or monocyte count for managing safety issues, he/she may order these tests as per regular site practice. AstraZeneca should be notified of all such cases without being revealed absolute eosinophil counts, absolute basophil counts, or absolute monocyte counts.
- Site staff who are directly involved in the participant's management should remain blinded to any eosinophil, basophil, and monocyte results included as part of an outside laboratory report or electronic medical record. To help ensure this, each investigational site will designate an individual (eg, administrator or another ancillary person) not directly involved in participant management, to receive and redact any eosinophil, basophil, and monocyte results prior to the report being handed over to the site staff involved in the participant's management and prior to filing the laboratory report as a source document. Similarly, eosinophil, basophil, and monocyte results must be redacted from all communications with AstraZeneca.
- CCI
[REDACTED]

After the primary DBL, restricted members of the study team will become unblinded to all participants' blood and biopsy cell counts obtained during the double-blind treatment period.

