- Participants randomised to the benralizumab 60 mg group will receive 2 benralizumab 30 mg injections
- Participants randomised to the placebo group will receive 2 placebo injections.

In the extension period, in order to maintain blinding to the benralizumab Q4W treatment regimen, participants that are randomised to receive benralizumab Q8W will also receive Q8W placebo injections at intervening visits where they are not scheduled to receive benralizumab (Figure 1).

The final dose of benralizumab/placebo will be administered at Week 48.

Figure 1 **Investigational Product Administration**

^a In the extension period, participants will receive benralizumab on a Q8W or Q4W dosing regimen, as predetermined at randomisation (Visit 2). Participants randomised to receive benralizumab Q8W in the extension period will also receive placebo at intervening study visits when they are not receiving benralizumab.

Q4W, every 4 weeks; Q8W, every 8 weeks.

Data Monitoring Committee: No

There is no data monitoring committee involved in the conduct of this study.

Statistical Methods

Approximately 160 participants will be randomised in a 3:3:3:3:4 ratio to different sequences of initial benralizumab dose or placebo, followed by Q4W or Q8W maintenance dosing with

benralizumab post Week 24 as described above. Randomisation will be stratified by region. Up to Week 24, ie, prior to start of the extension period evaluating Q4W and Q8W dosing regimens, participants in both benralizumab 60 mg initial dose treatment arms will be considered as a single treatment group (total n=60), as will participants in both benralizumab 30 mg initial dose treatment arms (total n=60).

By combining the treatment sequences with common initial benralizumab doses, the above randomisation will provide a 3:3:2 ratio across the benralizumab 60 mg and 30 mg initial dose groups and the placebo treatment arm (n=40), respectively, in order to assess the primary endpoint at Week 12. This provides 90% power for statistical significance at the 2-sided 2.5% level within each induction dose comparison versus placebo if the assumed effect is a 4.7 point mean difference in change in itch severity score over 7 days (ISS7) between benralizumab and placebo, assuming a standard deviation (SD) of 6 for the change in ISS7 and a 10% dropout rate.

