Post-menopause confirmation (FSH)	X	-	-	-	-	-	-	-	-	-	-	-	-	-	-	-	-	-	Section 8.2.1.1
Hepatitis/HIV screening	X	-	-	-	-	-	-	-	-	-	-	-	-	-	-	-	-	-	Section 8.2.1.2
Pharmacokinetics sample prior to IP administration	-	X	X	-	X	-	X	-	-	X	-	-	X	-	-	-	-	-	Section 8.5.1
Immunogenicity sample (ADA)	-	X	-	-	X	-	X	-	-	X	-	-	X	-	-	-	-	-	Section 8.5.2
CCI																			

Table 2 Schedule of Site Visit Activities

Procedure	Run-in	Double-blind placebo-controlled treatment period						Double-blind extension period						Follow-up		
Visit	1	2	3	4	5	6	7	8	9	10	11	12	13	14	15	16
Week ^a	-4 wk to -10 days ^b	0	4	8	12	16	20	24	28	32	36	40	44	48	52	60
IP administration ^f	-	X	X	X	X	X	X	X	X	X	X	X	X	X	-	-
CC1																
Skin biopsy	-	X	-	-	X	-	-	X	-	-	-	-	-	-	-	Section 8.6
Investigational product administration																
IP administration ^f	-	X	X	X	X	X	X	X	X	X	X	X	X	X	-	-

^a The window for Visits 3 through 16 will be \pm 3 days.

^b The run-in period is a maximum of 4 weeks and minimum of 10 days.

^c Unscheduled Visit: may be initiated as needed; procedures should be performed as clinically indicated at the discretion of the Investigator.

^d Investigational Product Discontinuation: In case of early discontinuation from investigational product, visit procedures should be performed 4 weeks \pm 7 days after the last dose of IP or as soon as feasible if this interval is missed (eg, if decision on discontinuation was made later). Note: The IPD visit replaces the nearest regular visit.

^e It is recommended that vital signs are assessed before any interventional study procedures (blood test collection, IP administration).

^f Review of self-administration of IP procedures may be offered at Visits 2 and 3.

ADA, Anti-drug antibodies; AE, Adverse Event; ECG, Electrocardiogram; EOT, End of treatment; FSH, Follicle-stimulating hormone; HIV, human immunodeficiency virus; IP, Investigational product; IPD, Investigational Product Discontinuation; PRO, Patient-reported outcomes.

All within-window PRO assessments (Table 3) that have not been completed prior to a site visit will be completed at the site before any other study procedures are conducted.

Table 3 Schedule of PRO Assessments

Instruments	Schedule
Daily PRO: UPDD Question 1	Every morning ^a . First assessment at home the day after Visit 1.
Daily PROs: UPDD Questions 2-7	Every evening ^b . First assessment at home on the day of Visit 1.

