4.1.2 Investigational Product Dosing Regimen

Participants who meet entry criteria will be randomised 3:3:3:3:4 by the interactive voice/web response system (Interactive Voice Response System [IVRS]/Interactive Web Response System [IWRs]) to one of the 5 treatment sequences described in Section [4.1](#).

[Figure 3](#) presents an overview of the IP that will be administered for each randomised treatment group.

Figure 3 Investigational Product Administration

^a In the extension period, participants will receive benralizumab on a Q8W or Q4W dosing regimen, as predetermined at randomisation (Visit 2). Participants randomised to receive benralizumab Q8W in the extension period will also receive placebo at intervening study visits when they are not receiving benralizumab.

Q4W, every 4 weeks; Q8W, every 8 weeks.

Dosing Regimen at Visits 2, 3, and 4 (Initial Double-blind 12-week Treatment Period)

All participants will receive randomised double-blind study medication Q4W at Visits 2, 3 and 4 (ie, Weeks 0, 4, and 8; [Figure 3](#)).

Dosing Regimen at Visits 5, 6, and 7

Participants randomised to receive either 60 mg or 30 mg benralizumab during the initial 12-week period will receive 30 mg benralizumab Q4W at Visits 5, 6 and 7 (ie, Weeks 12, 16 and 20; [Figure 3](#)).

Participants receiving placebo will continue to receive placebo ([Figure 3](#)).

Dosing Regimen at Visits 8 Through 14

At Week 24 (Visit 8), participants initially randomised to benralizumab 60 mg or benralizumab 30 mg will receive benralizumab 30 mg Q4W or Q8W according to their original randomisation at Week 2. Participants randomised to the Q8W regimen will receive placebo at Week 24 and benralizumab 30 mg at Week 28 ([Figure 3](#)).

At Weeks 24, 28, and 32 (ie, Visits 8, 9 and 10), participants initially randomised to placebo will receive benralizumab 30 mg Q4W. At Week 36 (ie, Visit 11), participants randomised initially to placebo will receive benralizumab 30 mg Q8W; these participants will receive placebo at Week 36 and benralizumab 30 mg at Week 40 (Visit 12) ([Figure 3](#)).

Participants transitioned to the benralizumab 30 mg Q8W dosing regimen will remain on the Q8W dosing regimen. Participants will continue to receive SC injections Q4W at the study site visits; thus, participants receiving benralizumab 30 mg Q8W will receive placebo at every other site visit ([Figure 3](#)).

The final dose of benralizumab or placebo will be administered at Week 48 (Visit 14).

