If 2 or more doses (consecutive or non-consecutive) of IP are missed, a conversation between the Investigator and the AstraZeneca study physician should take place to review treatment compliance and decide on the participant's further disposition. All participants, regardless of whether they remain on IP or not, will be encouraged to remain in the study through the end of the treatment period (Visit 16). Discontinuation procedures are described in Section 7.1.1).

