7 DISCONTINUATION OF STUDY INTERVENTION AND PARTICIPANT DISCONTINUATION/WITHDRAWAL

7.1 Discontinuation of Study Intervention

Participants who prematurely discontinue from IP will be asked to come in for all visits and study assessments at the IP Discontinuation (IPD)/EOT visit.

Discontinuation from IP does NOT automatically lead to a complete withdrawal from the study. Participants discontinuing from IP are strongly encouraged to continue in the study up to the study completion (Visit 17, Week 60) as described in Section 7.1.1.

Participants will be discontinued from IP in the following situations:

- Participant decision. The participant is at any time free to discontinue treatment, without prejudice to further treatment. The participant should always be asked about the reason(s) and presence of any AEs.
- AE that, in the opinion of the Investigator, contraindicates further dosing
- Severe non-compliance with the CSP
- Risk to participant as judged by the Investigator or AstraZeneca
- Pregnancy
- IP unblinding
- Development of any of the following study-specific criteria for discontinuation:
 - Anaphylactic reaction to IP administration, in the opinion of the Investigator, requiring administration of epinephrine
 - Development of helminth parasitic infestation requiring hospitalisation.

Refer to the SoA ([Table 2](#)) and Section 7.1.1 (IPD visit) for data to be collected at the time of IPD and follow-up and for any further evaluations that need to be completed.

The reason for premature discontinuation of IP should be documented in the source documentation and recorded in the eCRF.

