7.1.1.1 Early Discontinuation of Study Intervention

All participants who prematurely discontinue IP should return to the study site for IPD visit 4 weeks (\pm 7 days) after the last dose of IP for procedures, or as soon as feasible if this interval is missed (eg, if decision on discontinuation was made later), as described in [Table 2](#).

At the IPD visit, the participant will be offered the following options for further follow-up:

- Participants are encouraged to return to all scheduled site visits and perform all procedures/blood draws, but without IP administration, until end of the treatment period (Visit 16).
- If the participant is unwilling or unable to attend the scheduled site visits until the end of the double-blind treatment period, he/she will be offered a follow-up option that includes monthly telephone contact instead. During follow-up telephone contact, the Investigator will collect information about concomitant medications, information on CSU symptoms, and AE/SAE(s) (Section [8.3](#)).

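### The protocol gives conflicting visits for the last injection, end of treatment and study completion, and one section has injections after the Week 48 final dose

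*Protocol*

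**What the plan says.** **Last injection.** Protocol 6.3.2 reads "All participants will receive one SC injection at Visit 5 through Visit 16 (End of Treatment [EOT". Protocol 4.1.2 reads "The final dose of benralizumab or placebo will be administered at Week 48 (Visit 14", and SAP 1.1.2 gives the same week and visit. The synopsis agrees on the week: "The final dose of benralizumab/placebo will be administered at Week 48". In Table 2 the IP row is marked at Visits 2 to 14 and has dashes at Visits 15 and 16.

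**End of treatment.** Besides 6.3.2, Protocol 6.1.2 says that participants "will be encouraged to remain in the study through the end of the treatment period (Visit 16", and 7.1.1.1 has those who stop IP attend visits "until end of the treatment period (Visit 16". Table 2 places Visit 15 at Week 52 and Visit 16 at Week 60, under follow-up. Protocol 4.1 likewise separates a 52-week treatment period from a Week 60 follow-up visit.

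**Study completion.** Protocol 7.1 encourages participants who stop IP to continue "up to the study completion (Visit 17, Week 60". Table 2 has no Visit 17, and its window footnote stops at Visit 16: "The window for Visits 3 through 16 will be" ± 3 days.

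All of this is current operative text, not the amendment log.

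**The concern.** Section 6.3.2 states a dosing rule. It calls for injections at visits where Table 2 has none. Protocol 4.1.2 describes the regimen only up to Visit 14, so nothing says whether a later injection would be active or placebo.

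The date of the last dose and the meaning of EOT are used elsewhere:

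- The contraception, blood-donation and live-vaccine restrictions run for 12 weeks from the last dose (Protocol 5.1, 5.3, 6.5.4).
- The on-treatment AE period is bounded by the EOT visit and by the last dose plus 30 days (SAP 3.4.1).
- Participants who complete without a response are censored at EOT in the time-to-response analysis (SAP 3.3.5).
- ADA responses are evaluated through EOT (SAP 8.2).

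The follow-up of participants who stop IP also has three possible ends: Visit 16 (6.1.2, 7.1.1.1), Visit 17 at Week 60 (7.1), or Week 52 (Protocol 9.4.1 and SAP 4.1). The last two sections rely on that follow-up when they assume little missing data.

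**Working it through.** **Step 1: visit-to-week map (Table 2).** For Visits 2 to 15, week = 4 × (visit − 2). Visit 14 is therefore 4 × 12 = Week 48, and Visit 15 is 4 × 13 = Week 52. Visit 16 is listed as Week 60. This reproduces the Week 48 (Visit 14) pairing in Protocol 4.1.2 and SAP 1.1.2.

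**Step 2: injections per participant.** There are two injections at each of Visits 2, 3 and 4 (6.3.2) and one at each later dosing visit. The shifted row supposes that the Visit 16 in 6.3.2 means Week 52. Single injections then run from Week 12 to Week 52, which is (52 − 12)/4 + 1 = 11 visits.

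| Reading | Dosing visits | Injections | Last dose |
|---|---|---|---|
| Table 2, 4.1.2, SAP 1.1.2 | 3 + 10 = 13 | 3 × 2 + 10 = 16 | Week 48 |
| 6.3.2, shifted by one visit | 3 + 11 = 14 | 3 × 2 + 11 = 17 | Week 52 |
| 6.3.2, literal (to Visit 16) | 3 + 12 = 15 | 3 × 2 + 12 = 18 | Week 60 |

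Section 6.3.2 therefore adds one injection (last dose 52 − 48 = 4 weeks later) or two (60 − 48 = 12 weeks later). Neither reading agrees with a final dose at Week 48.

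**Step 3: on-treatment AE cut-off.** SAP 3.4.1 takes the earlier of the scheduled EOT visit and the last dose + 30 days. With study day = 7 × week + 1, Week 48 is day 337, Week 52 is day 365 and Week 60 is day 421.

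- Last dose Week 48, EOT Week 52: min(365, 367) = 365.
- Last dose Week 48, EOT Week 60: min(421, 367) = 367, a shift of 2 days.
- Last dose and EOT both Week 52: min(365, 395) = 365, no shift.
- Last dose and EOT both Week 60: min(421, 451) = 421, a shift of 56 days (8 weeks).

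The EOT label alone therefore moves the cut-off by about 2 days. The 8-week shift also needs the extra dosing to take place.

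**Step 4: restrictions after the last dose.** 48 + 12 = Week 60, which is the last scheduled visit. A last dose at Week 52 would carry them to Week 64, and one at Week 60 to Week 72. No visit is scheduled after Week 60.

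**Step 5: efficacy.** Weekly scores use the 7 days before the visit and leave out the visit day (SAP 3.2). On-site PROs are completed before IP (Protocol 6.1.1). An injection at the Week 52 visit cannot enter the Week 52 ISS7, UAS7 or HSS7. Week 12 is far earlier.

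**Step 6: time to response.** SAP 3.3.5 limits this analysis to Week 24 and Week 52, and SAP 4.2.7.5 makes it a descriptive Kaplan-Meier summary. Censoring non-responders later than Week 52 does not change the estimate at or before Week 52.

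**The case against.** The strongest reply is that 6.3.2 is one stray sentence in a blinding section and that other text controls dosing. Protocol 6.2.1 and 6.4 tie administration to Table 2, 6.3.3 has kits allocated by IVRS/IWRS, and 6.3.2 itself refers to 4.1.2 for the regimen. This stands as a limit on the consequence. A reader might infer that sites will give unscheduled injections; the documents support only the possibility.

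A second reply is that the stray labels agree with one another. Visit 16 as end of treatment and Visit 17 as Week 60 would fit a numbering with one more visit than Table 2. That is plausible, but the documents do not say so, and the Visits 2, 3 and 4 named in 6.3.2 match the current schedule. It would explain 6.1.2, 7.1 and 7.1.1.1. It would not rescue 6.3.2, because an injection at Week 52 still conflicts with a final dose at Week 48.

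A third reply is that the 12-week restrictions are defined from the last dose and so follow whatever dose is actually given. That is correct: those rules are not themselves in contradiction.

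**Conclusion.** The contradiction is real and has three parts: last injection (Visit 14 against Visit 16), end of treatment (Visit 16 against a 52-week period that ends at Visit 15), and completion (a Visit 17 that does not exist against Visit 16 at Week 60). Section 6.3.2 adds one to two injections per participant and moves the last dose by 4 to 12 weeks, depending on how its visit number is read.

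Stronger readings are tempting but not supported. The Week 52 weekly scores would not be contaminated (Step 5). The AE period does not move by eight weeks on the label alone (Step 3). The time-to-response estimates up to Week 52 do not depend on which week EOT means (Step 6). The Week 12 primary endpoint and the sample size are untouched. What remains is a wrong or unclear dosing-visit instruction and an unclear end of follow-up for participants who stop IP.

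Two assumptions apply. The IVRS/IWRS is taken to follow Table 2, which the documents imply but do not state. The 2-day figure uses the earlier-of rule for the overall on-treatment period; the separate extension-period sentence in SAP 3.4.1 names both limits without repeating that rule.

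**What to change.** Reconcile Protocol 6.1.2, 6.3.2, 7.1 and 7.1.1.1 with 4.1.2 and Table 2, so that one visit number and one week is stated for each of the last injection, EOT and study completion. State in the same place how long participants who stop IP are followed, and align Protocol 9.4.1 and SAP 4.1 with it. In SAP 3.3.5 and 3.4.1, state the week that EOT means. Which dosing statement is intended is for the sponsor to settle; this review does not propose one.

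The cost is wording in a protocol amendment and a short SAP clarification. No change to the sample size or the primary analysis is needed.
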